APPENDIX 3: ESTIMATES OF 1% OF THE PATIENT'S BLOOD VOLUME

Weight in	Weight in	Total	1% Total	Weight in	Weight in	Total Blood	1% Total
Kilograms	Pounds	Blood	Blood	Kilograms	Pounds	Volume	Blood
		Volume	Volume			mL	Volume
		mL	mL		48		mL
1	2.2	105	2.2	31 - 35	68 - 77	2480 - 2800	62 - 70
2	4.4	210	4.4	36 - 40	79 - 88	2880 - 3200	72 - 80
3	6.6	240	6.6	41 – 45	90 - 99	3280 - 3600	82 – 90
4	8.8	320	8.8	46 - 50	101 – 110	3680 - 4000	92 –100
5	11	400	11	51 – 55	112 - 121	4080 - 4400	102 –110
6	13.2	480	13.2	56 - 60	123 - 132	4480 - 4800	112 - 120
7	15.4	560	15.4	61 – 65	134 - 143	4880 - 5200	122 – 130
8	17.6	640	17.6	66 – 70	145 – 154	5280 - 5600	132 – 140
9	19.8	720	19.8	71 – 75	156 - 165	5680 - 6000	142 – 150
10	22	800	22	76 – 80	167 - 176	6080 - 6400	152 – 160
11 –15	24 - 33	880 - 1200	24 - 33	81 – 85	178 - 187	6480 - 6800	162 – 170
16 – 20	35 – 44	1280 - 1600	35 – 44	86 – 90	189 - 198	6840 - 7200	172 – 180
21 – 25	46 – 55	1680 - 2000	46 – 55	91 – 95	200 - 209	7280 - 7600	182 – 190
26 - 30	57 – 66	2080- 2400	57 – 66	96 - 100	211 - 220	7680 - 8000	192 - 200

Source: Usher et al, 1963

FINAL V3 10-AUG-2017 – US CONFIDENTIAL

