6.6. RISK-BENEFIT ASSESSMENT

ProvayBlueTM will be administered to the study patients to treat acquired methemoglobinemia resulting in a direct health benefit.

Refer to APPENDIX 1: US Package Insert of ProvayBlueTM for the risks associated with the use of ProvayBlueTM.

Entering a patient who requires methylene blue treatment, especially minors, into the protocol is associated with minimal incremental risk to the patient. The treating physician/Investigator and other treating health care professionals should continuously monitor the patient to ensure that the degree of burden and risk to the patient is minimized.

Extreme caution should be exercised when administering to newborns and infants below the age of 3 months due to lower concentrations of NADPH-methemoglobin reductase necessary for reducing methemoglobin to hemoglobin, making these infants more susceptible to methemoglobinemia produced by high doses of methylthioninium chloride.

The approximate volume of blood planned for collection from each patient over the course of the study presents no undue risk to the patients, nor does the collection of additional blood in the event an indwelling cannula is utilized (for wasting to ensure clean sample) or for recheck of safety labs, if deemed necessary by the Investigator.

As per regulations and guidelines, a limited volume of blood will be drawn from each patient during this study. Blood drawn from pediatric patients will not exceed the recommended maximum blood sampling volume for children in clinical trials which should not exceed 1% of total blood volume in one draw and 3% of total blood volume within a 4-week period (European Medicines Agency [EMA] guideline). Refer to APPENDIX 3: estimates of 1% of the patient's blood volume for the maximum volume of blood that can be drawn per patient. The number of attempts of venous punctures in children and adolescents will be restricted to a maximum of 3 attempts.

The safety data collected by this protocol (i.e., physical examination, vital signs, laboratory analysis [including metHb], and adverse event [AE]) are adequate to protect the patient's safety and should detect all expected treatment-emergent AEs (TEAEs).

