14. ASSESSMENTS OF PHARMACOKINETIC (PK)

Whenever feasible and ONLY if the total blood drawn for any patient does not exceed the recommended maximum blood sampling volume (refer also to Section 6.6 for regulation and guidance), PK samples are to be taken at the discretion of the Investigator based on the condition of the patient. The time blood sample(s) are taken should be recorded, but there is no absolute time window for the PK samples. Suggested PK sampling time points are as follows:

- Approximately 1 hour after the end of each ProvayBlueTM infusion (i.e. Dose 1, Dose 2 and any additional dose if applicable);
- Prior to Dose 2 (or any additional dose) ProvayBlueTM infusion (if applicable);
- Approximately 24 hours post the end of the last ProvayBlue™ infusion, or just prior to discharge from the clinic if earlier than 24 hours.

PK blood samples (venous) must be drawn from the arm opposite to the ProvayBlueTM dosing arm. Whole blood samples will be analyzed for methylene blue and azure B using a validated bioanalytical method. Arterial blood taken should be submitted for analysis with a note that it is an arterial sample.

Further instruction on PK sampling will be provided in a separate laboratory manual.

The volume of whole blood taken per venipuncture sample is no more than 2 ml. The number of samples drawn from any patient up to 2 years of age should be limited (refer also to Section 6.6 for regulation and guidance). Care should be taken to ensure that the maximum amount of blood drawn does not exceed what is stated in Section 6.6 (refer also to APPENDIX 3: estimates of 1% of the patient's blood volume) and in the PICD.

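### The 1% column in Protocol Appendix 3 is 2.1 to 2.75 times 1% of the blood volume printed beside it, so it contradicts the pediatric sampling limit it is meant to apply

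*Protocol*

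**What the plan says.** Protocol Section 6.6 (Risk-Benefit Assessment) sets the limit for children: sampling "which should not exceed 1% of total blood volume in one draw and 3% of total blood volume within a 4-week period". It then refers the reader to Appendix 3 "for the maximum volume of blood that can be drawn per patient". Section 14 (Assessments of Pharmacokinetic) repeats the instruction: "Care should be taken to ensure that the maximum amount of blood drawn does not exceed what is stated in Section 6.6", with a further reference to Appendix 3 and to the consent document. Section 14 also fixes the only sample volume given in the protocol: "The volume of whole blood taken per venipuncture sample is no more than 2 ml".

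Appendix 3 is headed "ESTIMATES OF 1% OF THE PATIENT'S BLOOD VOLUME". For each weight or weight band it prints the weight in kilograms, the weight in pounds, the total blood volume in mL, and a column labelled as 1% of total blood volume in mL.

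**The concern.** The appendix is the practical tool for applying the Section 6.6 limit, and its last column can be checked against the column beside it. At 10 kg the total is 800 mL, so 1% is 8 mL; the table lists 22 mL, which is also the weight in pounds. If the whole column is inflated in this way, a site that reads its maximum from the table is allowed more than twice what Section 6.6 permits per draw in children.

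This matters because patients of all ages are eligible, Section 6.6 itself urges particular care below 3 months of age, and methemoglobinemia already impairs oxygen delivery. Sampling is also repeated. Blood is scheduled at screening, within 1 hour after each infusion, before a second dose, at about 24 hours or discharge, and at the day 5-10 visit (Sections 12.1 to 12.4). Suggested PK samples come on top, and all of this falls inside one 4-week window.

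**Working it through.** **Inputs.** Weight, total blood volume (TBV) and the listed 1% value come from Appendix 3. The limits of 1% per draw and 3% in 4 weeks come from Section 6.6. The PK sample maximum of 2 mL comes from Section 14.

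**Step 1: how the listed column arises.**
- In all 14 rows from 1 to 30 kg it equals the weight in pounds: 1 kg is 2.2 lb and 2.2 mL; 10 kg is 22 lb and 22 mL; 26-30 kg is 57-66 lb and 57-66 mL.
- From 31 kg upward it equals 2 mL x kg: 31 x 2 = 62; 70 x 2 = 140; 100 x 2 = 200.
- The change of rule makes the listed maximum fall as weight rises, from 66 mL at 30 kg to 62 mL at 31 kg. A true 1% column could not do this, because TBV rises from 2400 to 2480 mL.

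The TBV column is regular: 105 mL/kg at 1-2 kg and 80 mL/kg above. The one exception is 86 kg, where 80 x 86 = 6880 mL but 6840 mL is printed. Patterns this regular in both columns are not a fault of reading the PDF.

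**Step 2: compare with true 1%.** True 1% = 0.01 x TBV; ratio = listed / true 1%.

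| Weight (kg) | TBV (mL) | True 1% (mL) | Listed 1% (mL) | Ratio |
|---|---|---|---|---|
| 1 | 105 | 1.05 | 2.2 | 2.10 |
| 2 | 210 | 2.1 | 4.4 | 2.10 |
| 3 | 240 | 2.4 | 6.6 | 2.75 |
| 5 | 400 | 4.0 | 11 | 2.75 |
| 10 | 800 | 8.0 | 22 | 2.75 |
| 11 | 880 | 8.8 | 24 | 2.73 |
| 30 | 2400 | 24.0 | 66 | 2.75 |
| 31 | 2480 | 24.8 | 62 | 2.50 |
| 35 | 2800 | 28.0 | 70 | 2.50 |
| 70 | 5600 | 56.0 | 140 | 2.50 |
| 100 | 8000 | 80.0 | 200 | 2.50 |

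The table has 46 weight endpoints (10 single weights plus both ends of 18 bands). Over all of them the smallest ratio is 2.095 and the largest 2.75. None is 1.

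**Step 3: against the two limits.** Because the ratio is taken to 1% of TBV, it is also the percentage of TBV that the listed volume represents.
- One draw at the listed volume: 2.1% to 2.75% of TBV. This is above the 1% per-draw limit and below the 3% limit.
- Two such draws: 2 x 2.095 = 4.2% to 2 x 2.75 = 5.5% of TBV. This is above the 3% limit in every row.

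**Step 4: what it changes at the bedside.** Volume left for hematology, biochemistry and metHb at the same draw after one 2 mL PK sample:

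| Weight (kg) | Left under true 1% (mL) | Left under the table (mL) |
|---|---|---|
| 1 | 1.05 - 2 = -0.95 (already over) | 2.2 - 2 = 0.2 |
| 2 | 2.1 - 2 = 0.1 | 4.4 - 2 = 2.4 |
| 3 | 2.4 - 2 = 0.4 | 6.6 - 2 = 4.6 |

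At 3 kg a single PK sample uses 2/2.4 = 83% of the true per-draw allowance. The table shows it using 2/6.6 = 30%.

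**The case against.** The arithmetic is not in dispute. The case on the other side is about consequence.

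- **The text limit still binds.** Section 6.6 states the 1% and 3% limits in words. Section 14 makes PK sampling conditional on the recommended maximum and also points to the consent document, which is not available here. The correct TBV is printed beside the wrong value. A site that observes every limit is held to the strictest. This stands: the table contradicts the rule but does not replace it.
- **No planned draw is shown to reach the listed volumes.** Only the PK volume is given, and on its own it exceeds true 1% only at 1 kg. Sample numbers up to 2 years of age are to be limited, and some draws are standard care. This also stands: over-sampling is possible but not demonstrated.
- **The limit is pediatric.** Rows at adult weights are arithmetically wrong but breach no stated limit. This stands.
- **The values might be per-patient totals.** Section 6.6 cites the appendix for the volume per patient, and every listed value is below 3% of TBV. However, both the title and the column heading say 1%, and the values are not 3% either (at 10 kg, 24 mL against 22 mL). This reading would make the heading wrong instead of the numbers, and a correction would still be needed.
- **The study is over.** The SAP (Section 1) reports enrollment closed on 31 August 2020 with 7 patients, and Section 3.1 says PK data were not obtained because samples were poorly handled. This limits the benefit of a correction to records, retrospective checks and reuse of the table.

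**Conclusion.** The concern holds. Every entry in the 1% column of Appendix 3 overstates 1% of the table's own total blood volume, by 2.1-fold at 1-2 kg, 2.73- to 2.75-fold at 3-30 kg, and 2.5-fold from 31 kg. Sections 6.6 and 14 both direct sites to this table, so a safety limit that the protocol relies on contradicts its own stated rule for children.

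The result needs no outside figure; it takes the printed TBV column as correct. The practical risk is concentrated in the smallest infants, where true allowances are a few millilitres. Whether any child was actually over-sampled cannot be determined, because volumes for hematology, biochemistry and metHb are not given, nor are the weights of the children enrolled, if any. The error bears on sampling safety only and does not touch any efficacy endpoint or analysis.

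**What to change.** 1. Recompute the column as 0.01 x TBV. Examples: 1.05 mL at 1 kg, 2.1 at 2 kg, 2.4 at 3 kg, 4.0 at 5 kg, 8.0 at 10 kg, 8.8-12.0 at 11-15 kg, 20.8-24.0 at 26-30 kg, 24.8-28.0 at 31-35 kg.
2. Add a 4-week column as 0.03 x TBV (3.15 mL at 1 kg, 7.2 at 3 kg, 24 at 10 kg), since Section 6.6 sets both limits and the appendix shows only one.
3. In Section 6.6, say which column is the per-draw limit and which the 4-week limit, that each covers all tubes taken and not only PK, and that both apply to pediatric patients.
4. Correct 6840 to 6880 mL in the 86-90 kg row, or explain it. This is a minor slip.
5. Check whether the consent document or laboratory manual took values from the table, and correct them if so.
6. As enrollment has closed, compare recorded draw volumes for any child enrolled with the true 1% and 3% values, report any excess as a deviation, and withdraw the present table from reuse.

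The document change is one page. Its cost is that fewer PK or laboratory samples are feasible in the smallest infants, which Section 6.6 already requires.

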1. INTRODUCTION AND SCOPE

ProvayBlue™ (methylene blue) was approved under the accelerated approval regulation, 21 CFR 314.510. Provepharm was required to conduct “further adequate and well-controlled studies” to verify and describe the clinical safety and benefit of the agent in therapeutic use for the treatment of acquired methemoglobinemia. To fulfill this requirement, Provepharm has initiated 2 studies and enrollment to both studies are closed at this time.

The first study, protocol PVP-2016003, titled “Open Label Clinical Study to Evaluate the Safety and Efficacy of ProvayBlue™ (Methylene Blue) for the Treatment of Acquired Methemoglobinemia,” was initiated 19 October 2017; the study had enrolled a total of 7 patients when the enrollment was closed on 31 August 2020. This study is referred to hereafter as the Interventional Study. Because of the slow pace of enrollment in this study, doubtless due to the paucity of patients with this ultra-rare disease available for assessment, a stand-alone database, as commonly utilized with clinical trials, has not been setup to capture the data; rather, all clinical data were captured on a paper case report form (CRF).

The second study, protocol HQF-METHB-2018001, titled “Use of Methylene Blue in Acquired Methemoglobinemia: Prospective Observational Registry (metHb),” started May 2018, and enrolled 24 patients before closure on 31 August 2020. This study is referred to hereafter as the Observational Study. The Observational Study was expected to last 2 years after the commencement of enrollment in up to approximately 50 hospital systems. This Observational Study was designed to support low-burden screening and data collection, and to enroll real-world cases of acquired methemoglobinemia treated with ProvayBlue™ without restriction; thus, study sites were more amenable to participate in this program than in the Interventional Study. When enrollment was closed, approximately 90 individual hospitals were approved to enroll patients into the Observational Study; however, only 24 patients were enrolled, again owing to the rarity of the clinical presentation of interest. An electronic database has been set up to house data from both studies.

Provepharm plans to combine the data from both studies in its report to FDA to satisfy the company’s first Post-Marketing Requirement (PMR-3065-1). This Data Summary Plan (DSP) is intended to provide a technical, detailed elaboration of the methods utilized to pool those 2 studies into a single database and to prepare an integrated summary of the data without inferential statistics. It is anticipated that the pooled results will be presented as a series of individual patient narratives with limited statistical analysis, befitting the observational nature of most of the data. The objective of this DSP is to assure that the methodologies to be used for summary are complete, accurate, and consistent.

In the development of this DSP, the following documents were used:

- Protocol PVP-2016003: final protocol dated 10 August 2017; CRF dated 04 December 2017

- Protocol HQF-METHB-2018001: final protocol dated 13 April 2019; CRF dated 04 May 2018
 - For the purpose of combining with data from Protocol PVP-2016003, the original CRF dated 04 May 2018 was updated on 27 October 2020

The principles in the following guidance documents have been followed in preparation of this DSP:

- International Conference on Harmonization (ICH) E3 (1995): Structure and Content of Clinical Study Reports
- ICH E6 (1996): Guideline for Good Clinical Practice
- ICH E9 (1998): Statistical Principles for Clinical Trials

In the event that a discrepancy is found between the descriptions in the statistical section of the protocols and this document, the description in this document supersedes the descriptions in the statistical section of the protocols.

A teleconference was held on 27 April 2020 between the sponsor and the agency. A post-meeting information package was submitted on 01 May 2020, in which metHb data collected from 13 patients (3 from PVP-2016003 and 10 from HQF-METHB-2018001) were summarized and presented to the agency. On 09 August 2020, the agency confirmed that the combined database was acceptable to be utilized to fulfill the post marketing requirement No. 1 (PMR1). This DSP was finalized after incorporation of the details of the meeting discussion and subsequent post-meeting communications between the sponsor and the agency.

2. OVERVIEW OF STUDY OBJECTIVES AND ASSESSMENTS

2.1. Study Objectives and Endpoints

An overview of study objectives and study endpoints is provided in Table 1. The Observational Study was designed to mirror the objectives, endpoints, and data collection elements of the Interventional Study, with modifications to (1) reflect the nature of observational data, where the specific timing of procedures and measurements is driven by institutional standard care, not a study protocol, and (2) to streamline the protocol and study procedures where possible.

Table 1: Overview of Study Objectives and Endpoints

Protocol Number	PVP-2016003 (Interventional Study)	HQF-METHB-2018001 (Observational Study)
Primary Objective	To confirm that ProvayBlue™ after a single administration is efficacious in patients with acquired methemoglobinemia	To confirm that ProvayBlue™ is efficacious in patients with acquired methemoglobinemia
Secondary Objectives	
 • To evaluate the efficacy of a single dose of 1 mg/kg of ProvayBlue™; • To evaluate the efficacy of a second dose of 1 mg/kg of ProvayBlue™ to further reduce metHb levels when metHb is not fully reduced by a single dose; • To evaluate the normalization of the respiratory rate, heart rate and blood pressure of patients who achieve a reduction in metHb level within 2 hours of receiving the first dose of ProvayBlue™; • To confirm the safety and tolerability of ProvayBlue™ injection in patients with acquired methemoglobinemia. 	To confirm the safety and tolerability of ProvayBlue™ in patients with acquired methemoglobinemia
Study Population	Patients who present in hospital/urgent care setting diagnosed with acquired methemoglobinemia. The population may include pediatric and adult patients (males and females of all ages are included).	Patients who are diagnosed in any care setting with acquired methemoglobinemia. The population may include pediatric and adult patients (males and females of all ages are included).

Protocol Number	PVP-2016003 (Interventional Study)	HQF-METHB-2018001 (Observational Study)
		
Primary Treated Group: At least ten (10) patients who are treated for acquired methemoglobinemia that is symptomatic (eg, exhibiting sleepiness, cyanosis, dizziness) and/or with measured methemoglobin levels $>30\%$
 
Secondary Treated Group: Up to ninety (90) additional asymptomatic patients who are treated for acquired methemoglobinemia with measured methemoglobin levels $\leq 30\%$

Safety Assessments	
 Physical examination; Vital signs; Hematology and biochemistry Electrocardiogram (ECG); Adverse events (AEs). 	Prevalence and nature of any adverse events occurring within 10 days of the administration of ProvayBlue™
Efficacy Endpoints	
 A reduction in metHb by 50% within 1 hour of dosing; Concomitant normalization of respiratory rate within 2 hours of the first dose of ProvayBlue™; Concomitant normalization of heart rate within 2 hours of the first dose of ProvayBlue™; Concomitant normalization of diastolic blood pressure (DBP) within 2 hours of the first dose of ProvayBlue™; Concomitant normalization of systolic blood pressure (SBP) within 2 hours of the first dose of ProvayBlue™. 	
 Time to reduction and magnitude of reduction in methemoglobin after administration of ProvayBlue™ for treatment of acquired methemoglobinemia. Time to normalization of the respiratory rate, heart rate, and blood pressure after administration of ProvayBlue™ for treatment of acquired methemoglobinemia Prevalence and nature of any adverse events occurring within 10 days

Protocol Number	PVP-2016003 (Interventional Study)	HQF-METHB-2018001 (Observational Study)
		
of the administration of ProvayBlue™
 
 • Prevalence of acquired methemoglobinemia cases by suspected causal agent • Resolution of methemoglobinemia-related symptoms during the index hospitalization
PK Endpoint	PK blood draws were planned and plasma concentrations of methylene blue and azure B were to be determined. However, PK data were not collected due to poor PK blood sample handling. Therefore, the PK endpoint will not be assessed.	None

2.2. Data Collection

2.2.1. HQF-METHB-2018001

Protocol HQF-METHB-2018001 is designed to be a low-burden minimal-risk **Observational Study**; data collection largely is by passive chart review, with follow-up by telephone or postal mail and/or using medical records where applicable. At some participating study sites, follow-up of acquired methemoglobinemia patients is standard care or part of quality improvement efforts, and some study sites are operating under a full waiver of consent / assent, based on local IRB approvals.

To minimize risk and qualify for the most streamlined study procedures, the **Observational Study** is electronic source (paper forms are not required) and the study data are de-identified to the HIPAA Safe-Harbor standard. Notably, the Safe-Harbor method involves collection of relative “study days” (eg, “Study Day 1, 12:45”) rather than absolute “calendar days” (eg, December 31, 2019, 12:45). Significantly, the “study day” safe-harbor format does not restrict any of the proposed analyses. In our proposed analyses, a pseudo enrollment date was created for each patient when the patient’s case was registered in the database.

To support intuitive and consistent presentation of the data, Study Day 1 Hour 0 is defined as the day and time of the completion of the first methylene blue infusion, and the timing of all study

measurements is presented as the relative time elapsed from this reference point. Thus, a negative relative time indicates that an event/assessment occurred prior to the first infusion completion time, whereas a positive relative time indicates that an event/assessment occurred after the first infusion conclusion time.

To gain understanding about all real-world cases of acquired methemoglobinemia treated with ProvayBlue™, and to encourage more sites to participate by making the enrollment criteria less restrictive, enrollment of a “Secondary Treated Group” was included in the Observational Study. That is, this study groups enrolled patients into two subgroups: Primary cases or Secondary cases.

All primary cases must fulfill the following requirements:

1. Baseline metHb $\geq 30\%$, OR
2. Documented signs or symptoms of methemoglobinemia with subsequent assay of methemoglobin levels above the institutional upper limit of normal (ULN). For these patients, response to the question ‘Were there any signs or symptoms judged to be clinically associated with the acquired methemoglobinemia?’ must be a ‘Yes’

Data from all Primary cases are fully monitored; inconsistencies are to be queried.

The Secondary Treated Group provides relatively sparse data on non-severe (asymptomatic with methemoglobin levels $< 30\%$) acquired methemoglobinemia cases that were nonetheless treated per clinical judgment with ProvayBlue™. Aside from verification of the inclusion criteria, data in these cases are not monitored.

